10.1.3. Plasma Pharmacokinetic Parameters Analysis

Dose proportionality will be tested using the power regression model for AUC_{0-inf} , AUC_{0-t} , and C_{max} of total and unbound PB2452 in Cohorts 4, 5, and 6.

A power model will be fit to describe the relationship between Y (C_{max} , AUC_{0-t} , and $AUC_{0-\infty}$) and X (dose) using the least-squares linear regression model [$\ln(Y) = \ln(\alpha) + \beta \ln(X)$, which is the logarithmic form of $Y = \alpha X^\beta$]. From each model, the intercept of regression line [$\ln(\alpha)$] and the slope of the regression line β will be presented along with the 90% confidence interval (CI) of the slope. This model will be fit for total and unbound PB2452 in Cohorts 4, 5, and 6. The dose proportionality will be declared when the 90% CI for β lies entirely within the critical region,

$$\left(1 + \frac{\ln(0.5)}{\ln(r)}, 1 + \frac{\ln(2.0)}{\ln(r)}\right)$$

where r is the ratio of the highest and the lowest dose included in the power model.

10.2. Urine Pharmacokinetics

10.2.1. Urine pharmacokinetic Concentrations

Pooled urine samples to assess urine ticagrelor and AR-C124910XX concentrations will be collected from subjects in Cohorts 4 through 10 over the following intervals: before dosing (within 60 minutes prior to the first ticagrelor dose on Day -2) and 0 to 6, 6 to 12, 12 to 24, and 24 to 48 hours after the initiation of the study drug infusion.

Urine concentration data will be listed by collection interval for each subject.

10.2.2. Urine Parameters

The following PK parameters for ticagrelor and AR-C124910XX concentrations in urine will be calculated whenever data permits:

Parameter	Description
Ae ₄₈	Total amount of drug excreted in urine from time 0 to 48 hours
Ae _{t1-t2}	Ae from time t1 to t2 hours where the values of t1 to t2 are 0 to 6, 6 to 12, 12 to 24, and 24 to 48
F _{e48}	Fraction excreted in urine from 0 to 48 hours after dosing
CL _{r48}	Renal clearance, calculated as Ae ₄₈ /AUC ₀₋₄₈

Additional urine PK parameters may be calculated, as necessary. Urine parameters will be listed by subject and summarized for each dose level using descriptive statistics (number of subjects, mean, SD, CV, median, minimum, and maximum).

11. Pharmacodynamic Analysis

The PD population will be used for all PD analysis tables and figures, except otherwise noted.

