The following plasma PK parameters will be calculated for AR-C124910XX using actual sampling times rather than scheduled sampling times:

- C_{max} ratio (metabolite:parent)
- AUC₀₋₂₄ ratio (metabolite:parent)

Urine:

Pooled urine samples to assess urine ticagrelor and AR-C124910XX concentrations will be collected from subjects in Cohorts 4 through 9 over the following intervals: before dosing (within 60 minutes prior to the first ticagrelor dose on Day -2) and 0 to 6, 6 to 12, and 12 to 24 hours after the initiation of the MEDI2452 (PB2452) infusion and 5th ticagrelor dose.

The following PK parameters for ticagrelor and AR-C124910XX concentrations in urine will be calculated:

- Total amount of drug excreted in urine (Ae)
- Ae from time t₁ to t₂ hours where the values of t₁ to t₂ are 0 to 6, 6 to 12, and 12 to 24 (Ae_{t1-t2})
- Fraction excreted in urine from 1 to 24 hours after dosing (Fe)
- Renal clearance (CLR)

Additional PK parameters may be generated, if needed.

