2.3. Exploratory

The exploratory objective is to evaluate the effect of MEDI2452 (PB2452) on the PK profile of unbound ticagrelor and unbound AR-C124910XX plasma concentrations.

3. Investigational Plan

This is a Phase 1, first-in-human, randomized, double-blind, placebo-controlled, single ascending dose, sequential group study to evaluate the safety, tolerability, PK, and PD of MEDI2452 (PB2452) with and without ticagrelor pretreatment when administered to healthy male and female subjects. All references to study drug within this statistical analysis plan (SAP) apply to MEDI2452 (PB2452) or matching placebo.

This study will have up to 10 cohorts and up to a total of 68 subjects with either 4 or 8 subjects in each cohort. The starting dose of MEDI2452 (PB2452) will be 100 mg and the planned doses for subsequent cohorts are 300, 1000, 3000, 9000, and 18000 mg. Other intermediate doses may also be tested but will not exceed 1800 mg.

The study will consist of a screening period (Days -45 to -4), check-in/pretreatment (Day -3 to Day -1), an in-house treatment period (Days 1 through 3 [Cohorts 1 through 8] or 4 [Cohorts 9 and 10]), and follow-up visits (Days 4, 7, and 28 [+2 days]). Subjects will receive an IV dose of study drug on Day 1.

On Day 1, subjects who meet all the inclusion criteria and none of the exclusion criteria will be randomly assigned to receive MEDI2452 (PB2452) or placebo in a ratio of 3:1 in all treatment cohorts as described below and as summarized in [Table 3-1](#).

Table 3-1 Summary of Treatment per Cohort

Cohort	Pre-MEDI2452 (PB2452) ticagrelor dosing to steady state (180 mg + 90 mg bid for 5 doses total)	MEDI2452 (PB2452) Dose (mg)	Number of subjects MEDI2452 (PB2452):placebo
1		100	3:1
2		300	3:1
3		1000	3:1
4	180 mg + 90 mg bid	1000	6:2
5	180 mg + 90 mg bid	3000	6:2
6	180 mg + 90 mg bid	9000	6:2
7	180 mg + 90 mg bid	18000	6:2
8	180 mg + 90 mg bid	18000	6:2
9	180 mg + 90 mg bid	18000	3:1 or 6:2*
10	180 mg + 90 mg bid	18000	3:1 or 6:2*

Abbreviations: bid, twice daily.

*Initially the cohort size will be 4 subjects (3:1); if needed for confirmation of PK/PD an additional 4 subjects (3:1) will be randomized in that same cohort.

Cohorts 1 to 3:

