- ^g Electrocardiograms will be obtained in triplicate for all subjects at screening, before dosing (within 1 hour prior to the initiation of the study drug infusion) and at 1 (±10 minutes), 4 (±10 minutes), 5 (±10 minutes), 24 (±30 minutes), and 48 hours (±30 minutes) after the initiation of the study drug infusion and on Days 7 and 28.
- ^h Cardiac telemetry monitoring will begin on Day -1 approximately 12 hours prior to the initiation of the study drug infusion (Hour 0) and will continue until the subject is discharged from the clinical site for Cohorts 1-10. For Cohorts 4-10, cardiac telemetry monitoring will begin on Day-3 (check in) approximately 12 hours prior to the first dose of Ticagrelor and will be removed once dosed with the initial dose of Ticagrelor.
- ⁱ For Cohorts 4 through 6 only: Beginning in the morning on Day -2, ticagrelor will be administered as a single oral dose of 180 mg, followed by 90 mg every 12 hours for 4 additional doses through Hour 0 (i.e., 5 total doses of ticagrelor). For Cohorts 7 through 10 only: Beginning in the morning on Day -2, ticagrelor will be administered as a single oral dose of 180 mg, followed by 90 mg every 12 hours for 4 additional doses through to Hour -2 (two hours prior to dosing at Hour 0) (i.e., 5 total doses of ticagrelor).
- ^k For all cohorts: MEDI2452 (PB2452) or placebo will be administered at Hour 0 of Day 1.
- ^l For timing of pharmacokinetic plasma samples for each cohort, refer to [section 3.5.1](#) of the protocol.
- ^q For Cohorts 4 through 10 only: Urine samples for PK analysis of ticagrelor and AR-C124910XX concentrations will be collected before dosing (within 60 minutes prior to the first ticagrelor dose on Day -2), and 0 to 6, 6 to 12, 12 to 24 and 24 to 48 hours after the initiation of the study drug infusion.
- ^r For timing of pharmacodynamic samples for each cohort, refer to [section 3.5.2](#) of the protocol.
- ^t Infusion site assessments will be performed for all subjects within 15 minutes prior to the initiation of the study drug infusion (Hour 0), and at 1, 3, 24, 48, and 72 hours after initiation of the study drug infusion and on Day 7.
- ^u For Cohorts 1 through 8 only.

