10.1. Plasma Pharmacokinetics

10.1.1. Plasma Pharmacokinetics Concentration

Blood samples for PK analysis of total and unbound PB2452 concentration in plasma will be collected from all subjects at the following time points: before dosing (0 hour) and up to 28 days after initiation of the study drug (PB2452 or placebo) infusion. Since ticagrelor is not administered to cohort 1-3 subjects, only unbound PB2452 concentration data will be collected for cohort 1-3 subjects. Specific collection times for each cohort relative to the initiation of the study drug (PB2452 or placebo) infusion on Day 1 are listed in the table below:

Summary of Pharmacokinetic Assessments for PB2452	
Cohorts 1-6	-10 minutes, 0.5, 1, 1.5, 2, 3, 4, 6, 8, 12, 24, 48, and 72 hours, and 7 and 28 days
Cohorts 7-8	-10 minutes 5 minutes and 0.25, 0.5, 1, 2, 3, 4, 6, 8, 8.25, 8.5, 9, 10, 11, 12, 16, 20, 24, 32, and 48 hours, and 7 and 28 days
Cohorts 9-10	-10 minutes, 5 minutes, 0.25, 0.5, 1, 2, 3, 4, 6, 8, 10, 12, 14, 16, 20, 24, 28, 32, 36, 48 hours, 7 and 28 days

Plasma samples for determining total and unbound concentrations of ticagrelor and its active metabolite AR-C124910XX, will be collected from subjects in Cohorts 4 through 10 at the following timepoints: before dosing (within 10 minutes prior to the initiation of the study drug infusion [Hour 0]), and up to 48 hours following the initiation of study drug infusion on Day 1. Of note, subjects in Cohorts 4-6 will be administered the 5th ticagrelor dose and study drug infusion simultaneously, whereas subjects in Cohorts 7-10 will be administered the 5th ticagrelor dose two hours before the study drug infusion initiation on Day 1.

Specific collection times for each cohort relative to the initiation of the study drug (PB2452 or placebo) infusion are listed in the table below:

Summary of Pharmacokinetic Assessments for Ticagrelor and Active Metabolite AR-C124910XX	
Cohorts 4-6	-10 minutes and 0.5, 1, 2, 3, 6, 12, 24 and 48 hours
Cohorts 7-8	-10 minutes, 5 minutes and 0.25, 0.5, 1, 2, 3, 6, 8, 10, 12, 14, 16, 20, 24, 32 and 48 hours
Cohorts 9-10	-10 minutes, 5 minutes, 0.25, 0.5, 1, 2, 3, 6, 8, 12, 14, 16, 20, 24, 28, 36 and 48 hours

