Additional PD parameters may be calculated, as necessary. Pharmacodynamic parameters will be listed by subject and summarized for each cohort using descriptive statistics (number of subjects, mean, SD, median, minimum, and maximum).

12. Changes in the Planned Analysis

For ECG measurements, QTcB interval will be calculated and a summary table for QTcF and QTcB values outside of pre-defined criteria will be produced.

13. Interim Analysis

There's no planned formal interim analysis for this study. Blinded safety data review for each dose cohort will be performed before dosing in the next cohort is allowed (Section 3.4.2.1 of the protocol).

Interim noncompartmental analyses of PK data and/or PK/PD modeling will be performed as needed.

14. Reference

Memo Re: PB2452-PT-CL-0001 Cohort 7 Dosing Regimen. To: [name], Principal Investigator, PPD Early Development Services; [name], Associate Director, Project Management, PPD Early Development. CC: [name], Project Manager, PPD Early Development. From: [name], Director, Clinical Operations. Date: July 3, 2018.

Memo Re: PB2452-PT-CL-0001 Cohort 8 Dosing Regimen. To: [name], Principal Investigator, PPD Early Development Services; [name], Associate Director, Project Management, PPD Early Development. CC: [name], Project Manager, PPD Early Development. From: [name], Director, Clinical Operations. Date: July 25, 2018.

Memo Re: PB2452-PT-CL-0001 Cohort9 and 10 Dosing Regimens. To: [name], Principal Investigator, PPD Early Development Services; [name], Associate Director, Project Management, PPD Early Development. CC: [name], Project Manager, PPD Early Development. From: [name], Sponsor Medical Consultant. Date: August 8, 2018.

15. Table of Contents: Tables, Listings and Figures

List of Tables	
Subject Disposition	
Table 14.1.1.	Subject Disposition
Demographics and Baseline Characteristics	
Table 14.1.2	Demographic and Baseline Characteristics (Safety Population)
Pharmacokinetics	
Table 14.2.1.1	Summary of Total Plasma PB2452 Concentrations (unit) (PK Population)
Table 14.2.1.2	Summary of Unbound Plasma PB2452 Concentrations (unit) (PK Population)
Table 14.2.1.3	Summary of Total Plasma Ticagrelor and AR-C124910XX Concentrations (unit) (PK Population)
Table 14.2.1.4	Summary of Unbound Plasma Ticagrelor and AR-C124910XX Concentrations (unit) (PK Population)

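### Fe48 names no ticagrelor dose as its denominator, and neither the fifth dose nor the five-dose total would make it a valid fraction excreted

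*SAP*

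**What the plan says.** SAP 10.2.2 opens with "The following PK parameters for ticagrelor and AR-C124910XX concentrations in urine will be calculated whenever data permits" and then lists Ae48, interval Ae, Fe48 and CLr48. CLr48 has a formula (Ae48 over AUC0-48). Fe48 has only the description "Fraction excreted in urine from 0 to 48 hours after dosing", with no formula and no dose.

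The timing comes from four other places:

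- **Urine collection (SAP 10.2.1):** "before dosing (within 60 minutes prior to the first ticagrelor dose on Day -2) and 0 to 6, 6 to 12, 12 to 24", then 24 to 48 h, counted from the start of the study drug infusion. The pre-first-dose sample is the only urine taken before Hour 0.
- **Regimen (SAP Table 3-1):** "ticagrelor dosing to steady state (180 mg + 90 mg bid for 5 doses total", that is 180 + 4 × 90 = 540 mg.
- **Fifth dose, Cohorts 4-6 (SAP 10.1.1):** "subjects in Cohorts 4-6 will be administered the 5th ticagrelor dose and study drug infusion simultaneously".
- **Fifth dose, Cohorts 7-10 (SAP Table 3-2, footnote i):** "followed by 90 mg every 12 hours for 4 additional doses through to Hour -2 (two hours prior to dosing at Hour 0".

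The supplied protocol (01 Feb 2018), section 3.5.1, lists "Fraction excreted in urine from 1 to 24 hours after dosing (Fe", also without a denominator. The SAP follows protocol amendment 5 of 03 August 2018, which was not supplied.

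**The concern.** A fraction excreted needs a numerator and a denominator that belong to the same dose or doses. Here they cannot be matched.

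- **Over 90 mg (fifth dose):** the numerator includes drug left from doses 1-4. In Cohorts 7-10 it also misses the first 2 h after the fifth dose.
- **Over 540 mg (all five doses):** the denominator counts 450 mg given before the fifth dose, but everything excreted before Hour 0 was never collected.
- **AR-C124910XX:** it is never dosed. Its mass over a ticagrelor dose is not a fraction unless both are put on a molar parent-equivalent basis, and the SAP states no basis.

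Two programmers following the text could produce values 540/90 = 6-fold apart, and neither would be what the label says. The timing change between Cohorts 6 and 7 also coincides with the step from 9000 to 18000 mg. A reader following Fe48 up the dose levels would therefore see a shift due to timing mixed with any effect of PB2452.

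**Working it through.** The plan gives no Fe48 value, so there is no figure to reproduce. The check asks how far each natural denominator lands from the true fraction.

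**Inputs from the SAP.** Doses of 180, 90, 90, 90 and 90 mg at -48, -36, -24, -12 and 0 h relative to the fifth dose. The urine window lasts 48 h and starts s hours after the fifth dose: s = 0 in Cohorts 4-6, s = 2 in Cohorts 7-10.

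**Assumptions (the documents give no half-life or absorption rate).** Linear one-compartment kinetics without PB2452; half-life 4, 6, 8, 10 or 12 h; ka 0.5, 1 or 2/h, or instantaneous.

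**Formula.** With k = ln 2 / half-life, the amount eliminated by x hours after a dose d is d × [1 − (ka·e^(−kx) − k·e^(−ka·x)) / (ka − k)], or d × (1 − e^(−kx)) if absorption is instantaneous. Sum over the five doses between s and s + 48. Bioavailability and the renal share of elimination multiply both this sum and the true fraction, so they cancel. The ratio to the true fraction is sum/90 or sum/540.

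**By hand, half-life 12 h, instantaneous absorption.**
- Left from doses 1-4 at the fifth dose: 180/16 + 90/8 + 90/4 + 90/2 = 11.25 + 11.25 + 22.5 + 45 = 90 mg. With the fifth dose, 180 mg is on board.
- Cohorts 4-6: 180 × (1 − 1/16) = 168.75 mg; 168.75/90 = 1.875.
- Cohorts 7-10: 180 × 2^(−2/12) = 160.36 mg at Hour 0; 160.36 × 15/16 = 150.34 mg; 150.34/90 = 1.670.

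**By hand, half-life 4 h, instantaneous absorption.**
- Left from doses 1-4: 0.04 + 0.18 + 1.41 + 11.25 = 12.88 mg, so 102.88 mg is on board.
- Cohorts 4-6: 102.85/90 = 1.143.
- Cohorts 7-10: 102.88 × 2^(−2/4) = 72.74 mg at Hour 0; 72.73/90 = 0.808.

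**Ae48/90 mg at ka 1/h:**

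| Half-life (h) | Cohorts 4-6 | Cohorts 7-10 |
|---|---|---|
| 4 | 1.173 | 0.949 |
| 6 | 1.374 | 1.176 |
| 8 | 1.580 | 1.396 |
| 10 | 1.768 | 1.594 |
| 12 | 1.929 | 1.765 |

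**Full grid, half-life 4-12 h:**

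| Quantity | Cohorts 4-6 | Cohorts 7-10 |
|---|---|---|
| Ae48/90 mg ÷ true fraction | 1.143-1.989 | 0.808-1.840 |
| Ae48/540 mg ÷ true fraction | 0.190-0.331 | 0.135-0.307 |
| Share of 0-48 h amount from doses 1-4 | 13-53% | 13-51% |
| Share of 540 mg eliminated before Hour 0 | 64-81% | 67-87% |
| Ae0-12/90 mg ÷ true fraction | 1.000-1.006 | 0.707-0.959 |

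In Cohorts 7-10 the direction of the error with 90 mg depends on the kinetics. At a 4 h half-life the ratio is 1.041, 0.949, 0.883 and 0.808 for ka 0.5, 1, 2 and instantaneous; from 6 h upward it is above 1 throughout.

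**Effect on Ae.** With a fixed denominator Fe48 is Ae48 times a constant, so Ae48 carries the same residue and offset. Cohorts 7-10 over Cohorts 4-6, from timing alone: 0.707-0.925 for Ae48 and 0.71-1.01 across the four interval amounts.

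**Longer half-lives.** Up to 24 h (ka 1/h or instantaneous), Ae48/90 mg reaches 2.33 in Cohorts 4-6 and 2.23 in Cohorts 7-10, Ae48/540 mg reaches 0.39, and Ae0-12/90 mg in Cohorts 4-6 falls to 0.89.

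**The case against.** The strongest reply is that this is a wording gap. Name the denominator, state a molar basis for the metabolite, label Fe48 as apparent, and move on. Within one cohort group a constant denominator cancels when PB2452 is compared with placebo, and SAP 4.1 keeps Placebo C4-C6 and Placebo C7-C10 apart outside the safety summaries. The sizes rest on assumed linear kinetics and apply directly to 12 to 14 placebo subjects (6 of 24 in Cohorts 4-6; 6-8 of 24-32 in Cohorts 7-10). Nothing is quantified for PB2452-treated subjects or for the metabolite.

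Most of that stands, and it limits the weight of the point. Naming a dose, however, only fixes reproducibility: either choice still gives a number that is not the fraction excreted.

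A reader might infer four stronger things that the documents do not support:

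- **That Ae is free of the problem.** It is not. Only the denominator problem is peculiar to Fe48.
- **That CLr48 is settled.** Its windows probably match, since plasma sampling in SAP 10.1.1 is timed from the infusion. But SAP 10.1.2 defines AUC0-48 as post-dose without saying which dose, and 10.2.2 does not say whether total or unbound AUC is used.
- **That the SAP departs from the protocol without declaring it.** Section 12 lists only "For ECG measurements, QTcB interval will be calculated and a summary table for QTcF and QTcB values outside of pre-defined criteria will be produced". The supplied protocol predates amendment 5, so whether the governing version still lists Fe, or defines its denominator, cannot be told.
- **That a mass ratio will be used for AR-C124910XX.** The SAP does not say so; this is a gap, not a demonstrated error.

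**Conclusion.** The point holds as a minor one. Fe48 is undefined as written, and neither 90 mg nor 540 mg makes it a valid fraction. That conclusion rests on the SAP's own dosing and collection times and on its stated aim of steady state.

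The sizes rest on the assumed model: 1.14-1.99 (Cohorts 4-6) and 0.81-1.84 (Cohorts 7-10) times the true fraction with 90 mg, and 0.13-0.33 times with 540 mg. They do not model PB2452 binding or metabolite kinetics, so they should not be carried over to PB2452-treated subjects, although the unmatched window and the uncollected urine are the same there.

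Fe48 is descriptive. No hypothesis test, escalation decision or primary objective uses it.

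Separately, SAP 2.2 and 8.2 allow for a sixth ticagrelor dose, while Tables 3-1 and 3-2 with footnote i show five. A dose on Day 2 would fall inside the 0-48 h window. This is a conditional inconsistency and is not needed for the conclusion above.

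**What to change.** 1. Drop Fe48 from SAP 10.2.2 and report interval Ae and CLr48, which are already planned. Confirm that the AUC0-48 used in CLr48 starts at Hour 0 like the urine, and state whether it is total or unbound.
2. Footnote Ae48 and interval Ae: they are amounts from several doses, carry residue of doses 1-4, and are not comparable between Cohorts 4-6 and Cohorts 7-10 (0.71-0.93 for Ae48 from timing alone in the assumed model). Compare PB2452 with placebo only within each cohort group.
3. If a fraction is wanted, report Ae0-12/90 mg for ticagrelor in the 6 Cohort 4-6 placebo subjects only. The 0-6 and 6-12 h collections supply it. State that it assumes near steady state: 1.00-1.01 of the true fraction for half-lives of 4-12 h, down to 0.89 at 24 h. Do not extend it to Cohorts 7-10 (0.71-0.96 for 4-12 h). Any fraction for AR-C124910XX needs a stated molar parent-equivalent basis.
4. Declare the removal in SAP section 12 if amendment 5 still lists Fe.
5. Reconcile the sixth-dose passages with the five-dose tables.

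The cost is SAP wording and a small programming change, with no new samples. The downside is that there would be no fraction-excreted figure for PB2452-treated subjects or for anyone in Cohorts 7-10, and at most 6 subjects with a ticagrelor fraction.

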11.1. Pharmacodynamic Data

Blood samples for PD analysis will be collected from subjects in Cohorts 4 through 10 at the following time points: before dosing (within 60 minutes prior to 1st ticagrelor dose on Day -2) and again before dosing (within 10 minutes prior to the initiation of the study drug infusion [Hour 0]), and up to 48 hours after the initiation of study drug infusion. Specific collection times are listed in the table below:

Summary of Pharmacodynamic Assessments	
Cohorts 4-6	Day -2 (60 minutes prior to 1 st ticagrelor dose) and Day 1 (-10 minutes, 0.5, 1, 2, 3, 6, 12, 24 and 48 hours)
Cohorts 7-8	Day -2 (60 minutes prior to first 1 st dose) and Day 1 (-10 minutes, 5 minutes and 0.25, 0.5, 1, 2, 3, 6, 8, 10, 12, 16, 20, 24 and 48 hours)
Cohort 9-10	Day -2 (60 minutes prior to first ticagrelor dose) and Day 1 (-10 minutes, 5 minutes, 0.25, 0.5, 1, 2, 3, 6, 8, 12, 16, 20, 24, 28, 36 and 48 hours)

Platelet aggregation will be assessed using the LTA, VerifyNow, and VASP assays. The results of platelet aggregation from the LTA assay (using 5 μ M ADP and 20 μ M ADP) will be expressed as maximal-extent aggregation (MA), %baseline MA, final-extent aggregation (FA) and %baseline FA, which will be calculated from the platelet aggregation-time profile for each sampling time point. The results for the VerifyNow assay will be expressed as PRU and %baseline PRU, which will be calculated from the platelet aggregation-time profile for each sampling time point. Similarly, PD results from the VASP assay will be expressed as PRI and %baseline PRI, which will be calculated from the platelet aggregation-time profile for each sampling time point. PD data will be listed by subject with ADA status and summarized for each treatment group for each time point using descriptive statistics (number of subjects, mean, SD, median, minimum, and maximum). A ADA-positive subject is defined as a subject with at least one ADA-positive sample at any time during the treatment or follow-up observation period. In case of a positive pre-treatment sample, if the titer of at least one post-treatment ADA is elevated at least 2 folds of the titer in pre-treatment sample, this subject is also ADA positive otherwise ADA negative.

Mean PD data versus scheduled time profiles will be presented graphically.

Scatter plots of PD data versus total and unbound PB2452 plasma concentrations will be prepared for all cohorts, as appropriate. A box plot of PD data versus sampling time point will be prepared for each dose level.

Correlation between LTA assay, VerifyNow assay and VASP assay will be investigated graphically. Scatter plots of individual subject MA versus PRU (5 μ M ADP and 20 μ M ADP), MA versus PRI (5 μ M ADP and 20 μ M ADP), and PRU versus PRI will be plotted, and the correlation coefficient r (Spearman's rank correlation coefficient) and p -value will be displayed.

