11.2. Pharmacodynamic Parameters

Pharmacodynamic parameters will be calculated using actual timepoints using SAS[®] Version 9.3 or higher. Missing PD values will be treated as missing for PD parameter calculation.

The following PD parameters will be calculated using %baseline/actual MA and FA data, as appropriate, from the LTA assay for both the 5 μ M and 20 μ M ADP conditions.

Parameters following study drug infusion:	
APA _{max}	Maximal actual platelet aggregation
PA _{max}	Maximal percent of baseline platelet aggregation
TPA _{max}	Time to maximal actual platelet aggregation
TPA _{60%}	Time to 60% of baseline platelet aggregation, calculated as the first time point when %baseline platelet aggregation reaches 60% or above.
TPA _{80%}	Time to 80% of baseline platelet aggregation, calculated as the first time point when %baseline platelet aggregation reaches 80% or above
TPA _{90%}	Time to 90% of baseline platelet aggregation, calculated as the first time point when %baseline platelet aggregation reaches 90% or above

The following PD parameters will be calculated using %baseline/actual PRU data from the VerifyNow assay.

Parameters following study drug infusion:	
PRU _{max}	Maximal actual PRU
TPRU _{max}	Time to maximal actual PRU
TPRU ₂₀₀	Time to 200 or higher PRU, calculated as the first time point when the actual PRU reaches 200 or above
TPRU _{60%}	Time to 60% of baseline PRU, calculated as the first time point when %baseline PRU reaches 60% or above
TPRU _{80%}	Time to 80% of baseline PRU, calculated as the first time point when %baseline PRU reaches 80% or above
TPRU _{90%}	Time to 90% of baseline PRU, calculated as the first time point when %baseline PRU reaches 90% or above

The following PD parameters will be calculated using %baseline/actual PRI data from the VASP assay.

Parameters following study drug infusion:	
APRI _{max}	Maximal actual PRI
PRI _{max}	Maximal percent of baseline PRI
TPRI _{max}	Time to maximal actual PRI
TPRI _{60%}	Time to 60% of baseline PRI, calculated as the first time point when %baseline PRI reaches 60% or above
TPRI _{80%}	Time to 80% of baseline PRI, calculated as the first time point when %baseline PRI reaches 80% or above
TPRI _{90%}	Time to 90% of baseline PRI, calculated as the first time point when %baseline PRI reaches 90% or above

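### Time-to-threshold PD parameters are tabulated by cohort although sampling starts at 0.5 h in Cohorts 4-6 and at 5 minutes in Cohorts 7-10, so rapid onset times are not comparable between the two blocks

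*SAP*

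**What the plan says.** SAP 11.1 sets the PD sampling times by block, counted from the start of the study drug infusion. In each list the leading 10 minutes is the sample before infusion.

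- Cohorts 4-6: "10 minutes, 0.5, 1, 2, 3, 6, 12, 24 and 48 hours". That is 8 samples after infusion start, the first at 0.5 h.
- Cohorts 7-8: "10 minutes, 5 minutes and 0.25, 0.5, 1, 2, 3, 6, 8, 10, 12, 16, 20, 24 and 48 hours". That is 14 samples, the first at 5 minutes.
- Cohorts 9-10: "10 minutes, 5 minutes, 0.25, 0.5, 1, 2, 3, 6, 8, 12, 16, 20, 24, 28, 36 and 48 hours". That is 15 samples, the first at 5 minutes.

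SAP 11.2 defines the onset parameters by first observed crossing. For LTA at 80% it reads: "Time to 80% of baseline platelet aggregation, calculated as the first time point when %baseline platelet aggregation reaches 80% or above". The 60% and 90% versions, the PRU and PRI versions and the time to a PRU of 200 follow the same rule. The maxima, such as "Maximal percent of baseline platelet aggregation", carry no restriction on which samples count. On timing, "Pharmacodynamic parameters will be calculated using actual timepoints". The parameters are then "summarized for each cohort using descriptive statistics", in Tables 14.2.6.1-3.

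SAP 11.1, 11.2 and 12 give no common set of times, no interpolation or interval censoring, and no caution about the unequal schedules. SAP 11.1 does separately summarize the PD values by treatment group at each time point.

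**The concern.** LTA effectiveness across ascending doses is a primary objective (SAP 2.1), and speed of reversal is one of the things a reader will look for in Tables 14.2.6.1-3. A first-crossing time cannot be shorter than the time of the first sample. The sampling schedule changes exactly where the dose rises from 9000 to 18000 mg and the infusion regimen changes. A shorter tabulated onset in Cohorts 7-10 could therefore come partly from looking earlier, and the table would not show it. What is at stake is the reading of a descriptive table. No formal test or decision rule rests on it.

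**Working it through.** The plan states no figure on this point, so there is none to reproduce. The inputs are the three sampling lists in SAP 11.1 and the definitions in SAP 11.2.

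**1. Direction.** All 8 Cohort 4-6 times (0.5, 1, 2, 3, 6, 12, 24, 48 h) are also scheduled in Cohorts 7-8 and 9-10, so the early grid is a strict subset of both later grids. For one and the same subject profile, a later grid can only give an equal or earlier first crossing and an equal or higher maximum. This needs no distributional assumption.

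**2. Recorded onset at scheduled times.** Recorded onset is the first grid time at or after the true crossing, if the response stays above threshold.

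| True crossing | Cohorts 4-6 | Cohorts 7-10 | Gap |
|---|---|---|---|
| up to 5 min | 30 min | 5 min | 25 min |
| over 5 to 15 min | 30 min | 15 min | 15 min |
| over 15 to 30 min | 30 min | 30 min | 0 |
| over 0.5 to 6 h | same | same | 0 |

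The last row holds because every grid has 0.5, 1, 2, 3 and 6 h in that range and nothing else.

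**3. Simulation with identical true response.** Assumptions, not in the documents: aggregation rises from 20% of baseline to a plateau of 95%, with independent within-subject noise of SD 5 or 10 points; 100,000 subjects per scenario.

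- Rapid onset (time constant 0.1 h, SD 5): median time to 60% is 0.50 h in Cohorts 4-6 against 0.08 h in Cohorts 7-10. Median time to 80% is 0.50 against 0.25 h. For 90% the medians are both 0.50 h and the means 0.63 against 0.47 h.
- Slow onset (time constant 1 h): times to 60% and 80% are practically equal (means 1.06 and 2.16 h on all grids at SD 5). The mean time to 90% is 4.3-4.7 h against 3.9-4.0 h.

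**4. Late crossings.** After 6 h the later grids add times, so a late recovery as ticagrelor wears off can also be recorded earlier. With no reversal and an assumed gradual recovery (SD 5), the median time to 60% is 48 h in Cohorts 4-6 and 7-8 against 36 h in Cohorts 9-10, which have samples at 28 and 36 h. This is ticagrelor offset, not onset of reversal.

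**5. Maxima.** On a flat response with independent normal noise, E(max of n) = ∫ x·n·φ(x)·Φ(x)^(n−1) dx, in noise SD:

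- n = 8: 1.42
- n = 14: 1.70, a gap of 0.28
- n = 15: 1.74, a gap of 0.31 (from unrounded values)

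In the simulation, the rapid sustained case at SD 5 gives mean maxima of 102.1 against 103.1 and 103.3. A transient effect gives a gap of only 0.1-0.5 points. Slow onset gives 1.9-4.0 points over the two noise levels, about 0.3 to 0.4 SD.

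**6. Is a crossing before 15 minutes plausible in Cohorts 4-6?** Protocol 1.3 expects 1000 mg to be the minimally active dose. SAP 7.3 gives 1000, 3000 and 9000 mg over 30 minutes. At an assumed constant rate these are 33.3, 100 and 300 mg/min, so 1000 mg has been delivered at 30, 10 and 3.3 minutes. On this rough guide early crossing is unlikely in Cohort 4 but possible in Cohorts 5 and 6.

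**The case against.** The case on the other side is substantial.

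- *A like-for-like view already exists.* Tables 14.2.5.1-3, the mean profiles and the box plots show the PD data by sampling time, and every Cohort 4-6 time is present in the later cohorts. This stands. These outputs are unaffected, but they do not correct the derived onset times.
- *Nothing is tested between cohorts.* The PD parameters are descriptive, with 3 to 6 active subjects per cohort. This stands and limits the severity.
- *Placebo is split into C4-C6 and C7-C10.* Each placebo group shares its block's early sampling, which helps active-versus-placebo reading within a block. It does not help active cohorts read across blocks. SAP 4.1 also says placebo is pooled for all presentations.
- *Earlier onset in Cohorts 7-10 may be real.* Cohort 7 receives 3000 mg in 5 minutes and Cohorts 8-10 receive 6000 mg in 15 minutes, so an identical response is not the expected case. This stands. It means the schedule part and the true part are mixed, not that the schedule part is absent.
- *The counts depend on time zero.* SAP 11.2 labels the parameters as following the infusion. Infusions last 8 h (Cohort 7), 12 h (Cohort 8) and 16 h 20 min (Cohorts 9-10), leaving 6, 4 and 5 samples after their end, against 7 in Cohorts 4-6. SAP 11.1 counts from infusion start, which is the likelier meaning, but 11.2 should say so.

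A reader might go further and infer that the later cohorts must look faster and higher through sampling alone, by a factor of six. The documents do not support that. Six is only the ratio of the earliest recordable times (30/5). It would need a crossing within 5 minutes, and at 3 minutes Cohorts 4-6 would have received only 100, 300 or 900 mg at a constant rate. Nor do the times to maximum look faster: in the rapid sustained simulation at SD 5 their means were 12.3, 12.6 and 15.8 h for Cohorts 4-6, 7-8 and 9-10.

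**Conclusion.** The point holds for the threshold times when onset is rapid, and it is minor. A lasting crossing within 15 minutes of infusion start is recorded 15 to 25 minutes later in Cohorts 4-6 than in Cohorts 7-10. For crossings between 15 minutes and 6 h the scheduled times agree and the effect on onset is small. The maxima are pushed upward in Cohorts 7-10 only slightly: near 0 for a transient effect, about 0.3 noise SD on a flat response, and up to about 0.4 SD with slow onset. These sizes rest on assumed profiles and independent noise. The documents give no assay SD, so they cannot be put in clinical terms.

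The ordering is certain for a single profile. It is not certain for a mean over only those subjects who reach the threshold, because denser sampling also adds late reachers.

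It would be wrong to infer that the primary LTA objective is compromised, since the by-time-point summaries remain comparable. The single PD grid in the supplied Protocol (01 Feb 2018) is no contradiction either: the SAP follows amendment 5.

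**What to change.** In SAP 11.2:

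- Add a second derivation of the threshold-time parameters for LTA, PRU and PRI, and secondarily of the maxima. Use only samples at the scheduled times shared by all cohorts: 0.5, 1, 2, 3, 6, 12, 24 and 48 h after infusion start.
- Use that version for any side-by-side reading of Cohorts 4-6 against 7-10. Keep the full-grid values for description within Cohorts 7-8 and within Cohorts 9-10.
- Footnote each cohort's first sampling time in Tables 14.2.6.1-3, and state that times run from the start of infusion.
- State that dose, infusion profile and timing after the 5th ticagrelor dose (simultaneous in Cohorts 4-6, 2 hours earlier in Cohorts 7-10) still differ between the blocks. The common grid removes only the schedule artefact.

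With identical responses, every cohort then has 8 samples and an earliest recordable onset of 0.5 h, so the schedule-driven gap is zero. The cost is SAP wording and one extra derivation, with no new samples. In that version onset resolution in Cohorts 7-10 is coarser, and rapid responders become ties at 0.5 h.
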